9.2 Responsibility for Analyses/In-house Blinding

The statistical analysis of the data obtained from this study will be the responsibility of the Clinical Biostatistics department of the Sponsor.

The base study will be conducted as a double-blind study under in-house blinding procedures. The official database will not be unblinded until medical/scientific review has been performed, protocol deviations have been identified, and data have been declared final and complete. The first database lock will be executed, and a study report will be written reporting of the test of the primary and secondary efficacy hypotheses when at least 17 confirmed cases for each primary endpoint and secondary endpoint have been accumulated. After the first database lock for primary analysis, data for immunogenicity and safety endpoints will continue to be collected, and additional database locks will be executed, including a second database lock for the final efficacy analysis after the completion of the final sample assessment for efficacy in the base study and a final database lock of the base study for the final immunogenicity and safety analysis after the last participant's Final Visit in the base study. A report will be written after each database lock. Participants will be unblinded after the initial database lock to determine eligibility for participation in the extension study.

The Clinical Biostatistics department will generate the randomized allocation schedule(s) for study treatment assignment. Randomization will be implemented in an IRT system.

9.3 Hypotheses/Estimation

Objectives and hypotheses of the study are stated in Section 3. Data in the first database lock will be used for hypothesis testing.

9.4 Analysis Endpoints

9.4.1 Efficacy Endpoints

Primary efficacy endpoint

HPV 6/11/16/18-related anogenital persistent infection is defined to have occurred if any of the following occurs:

- The participant is positive by an HPV PCR assay (type 6, 11, 16, or 18) to at least 1 common gene for the given vaccine HPV type in anogenital or biopsy samples collected in two or more consecutive visits 6 months (± 1-month window) apart (The minimum length of time between samples for a participant to be counted as a case of persistent infection is 4 months); OR
- The participant has Pathology Panel consensus diagnosis of genital warts, PIN, penile, perianal or perineal cancer AND detection of HPV 6, 11, 16 or 18 by Thinsection PCR in an adjacent section of the same biopsy block AND is PCR positive for the same HPV type to at least 1 common gene in the sample obtained at a separate adjacent visit with regardless of visit interval, prior to or following the biopsy showing HPV disease.

Secondary efficacy endpoint

HPV 31/33/45/52/58-related anogenital persistent infection is defined to have occurred if any of the following occurs:

- The participant is positive by an HPV PCR assay (type 31, 33, 45, 52 or 58) to at least 1 common gene for the given vaccine HPV type in anogenital or biopsy samples collected in two or more consecutive visits 6 months (± 1-month window) apart (The minimum length of time between samples for a participant to be counted as a case of persistent infection is 4 months); OR
- The participant has Pathology Panel consensus diagnosis of genital warts, PIN, penile, perianal or perineal cancer AND detection of HPV 31, 33, 45, 52 or 58 by Thinsection PCR in an adjacent section of the same biopsy block AND is PCR positive for the same HPV type to at least 1 common gene in the sample obtained at a separate adjacent visit with regardless of visit interval, prior to or following the biopsy showing HPV disease.

Exploratory efficacy endpoints

- HPV 6/11/16/18/31/33/45/52/58-related anogenital persistent infection detected in samples from two or more consecutive visits 6 months (± 1-month window) or longer apart.
- HPV 6/11/16/18/31/33/45/52/58-related genital warts, PIN, penile, perianal or perineal cancer

PROTOCOL/AMENDMENT NO.: 064-03

HPV 6/11/16/18/31/33/45/52/58-related intra-anal persistent infection detected in samples from two or more consecutive visits 6 months (± 1-month window) or longer apart.

• HPV 6/11/16/18/31/33/45/52/58-related anogenital persistent infection detected in samples from three or more consecutive visits 6 months (± 1-month window) or longer apart (i.e., at least 12 months persistent infection)

These endpoints will be also evaluated for each HPV types.

9.4.2 **Immunogenicity Endpoints**

GMT to each of HPV 6, 11, 16, 18, 31, 33, 45, 52, and 58 at 1 month post last dose (Month 7) based on cLIA using serum samples.

Seroconversion to each of HPV 6, 11, 16, 18, 31, 33, 45, 52, and 58 at 1 month post last dose (Month 7) based on cLIA using serum samples. Seroconversion is defined as changing a participant's serostatus from seronegative at Day 1 to seropositive at 1 month post last dose (Month 7). A participant with anti-HPV cLIA titer at or above the serostatus cutoff of the cLIA for a given HPV type is considered seropositive for that HPV type.

9.4.3 **Safety Endpoints**

- Solicited injection-site AEs and elevated temperatures during Days 1 through 5 postvaccination
- Systemic AEs and SAEs during Days 1 through 15 postvaccination
- Serious vaccine-related AEs observed any time during the study

9.5 **Analysis Populations**

In efficacy and immunogenicity analysis populations, participants are analyzed in the vaccination group to which they were randomized (i.e., as-randomized). In safety analysis population, participants are analyzed according to the vaccination regimen actually received (i.e., as-treated).

9.5.1 **Efficacy Analysis Populations**

Per-Protocol Efficacy (PPE) Population

The PPE population will serve as the primary population for the analysis of efficacy in this study. To be included in the per-protocol population, participants must:

- 1. Have received all 3 vaccinations with the correct dose of the correct clinical material within 1 year.
- 2. Have Month 7 swab samples collected within 14 to 72 days post dose 3 with non-missing PCR result.

- 3. Be seronegative to the appropriate HPV type(s) at baseline and PCR-negative to the appropriate HPV type(s) on all swabs and biopsies (if collected) from baseline through Month 7.
- 4. Have no other protocol violations that could interfere with the evaluation of efficacy.

The final determination on protocol violations, which will be used for determining the PPE population, will be made prior to the database lock and will be documented in a separate memo or the sSAP.

HPV Type-Specific Naïve (HN-TS) Population

The HN-TS population will serve as a supportive population for the analysis of efficacy in this study. To be included in the HN-TS population, participants must:

- 1. Have received at least 1 vaccination,
- 2. Be seronegative and PCR-negative to appropriate HPV type(s) at Day 1.

Participants who receive incorrect clinical material or an incorrect dose of vaccine will be included in the vaccination group to which they were randomized. Protocol violations that could interfere with the evaluation of efficacy will not cause participants to be excluded from the HN-TS population.

For each of the PPE and HN-TS analysis populations, to be included in the analysis population with respect to either HPV type 6 or 11, participants must be HPV-negative at the relevant time point(s) for both HPV 6 and 11. To be included in the analysis populations with respect to any other vaccine HPV type, participants need to be HPV-negative at the relevant time point(s) only for the HPV type under evaluation.

In the PPE population, efficacy endpoints are counted starting after Month 7 (after 1 month post dose 3). In the HN-TS population, efficacy endpoints are counted starting after Day 1.

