3 HYPOTHESES, OBJECTIVES, AND ENDPOINTS

Hypotheses are aligned with objectives in the Objectives and Endpoints table.

The following objectives and endpoints will be evaluated in Japanese males, 16 to 26 years of age.

Primary Objective	Primary Endpoint
Objective: To demonstrate that a 3-dose regimen of the 9vHPV vaccine will reduce the combined incidence of HPV 6/11/16/18-related anogenital (external genital and intra-anal) persistent infection detected in samples from two or more consecutive visits 6 months (± 1-month window) or longer apart compared with placebo in participants who are seronegative at Day 1 and PCR-negative Day 1 through Month 7 to the relevant HPV type.	HPV 6/11/16/18-related anogenital persistent infection
Hypothesis: Administration of a 3-dose regimen of the 9vHPV vaccine reduces the combined incidence of HPV 6/11/16/18-related anogenital persistent infection detected in samples from two or more consecutive visits 6 months (± 1-month window) or longer apart compared with placebo (The statistical criterion for success requires that the lower bound of the 2-sided 95% CI of vaccine efficacy is >0%).	
Objective: To evaluate the safety and tolerability of the 9vHPV vaccine.	-Solicited injection-site adverse events (AEs) -Systemic AEs -Serious adverse events (SAEs)

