Participants will be followed for solicited injection-site AEs Days 1 through Days 5 following each vaccination, and any other injection-site AEs and systemic AEs Days 1 through Days 15 following each vaccination. Any SAEs regardless of causality will be recorded from the time of randomization through 6 months postdose 3. Vaccine-related SAEs and deaths will be collected throughout the study. New medical conditions (defined as incident medical conditions occurring outside of Days 1 to Days 15 period following each vaccination and not considered SAEs) will be recorded for all participants at each study visit throughout the study.

The primary analysis is case driven. The database will be locked, and the primary analysis will be conducted after at least 17 primary efficacy endpoint cases and at least 17 secondary efficacy endpoint cases have been observed in the base study. There is no interim analysis planned in this study. These efficacy results as well as immunogenicity and safety results based on data in the initial database lock for the primary analysis will be reported as the primary CSR. All participants will be unblinded after the primary efficacy analysis database lock. Once a participant is unblinded, no further efficacy samples will be collected from the participant.

Once at least 17 primary endpoint cases and at least 17 secondary efficacy endpoint cases are accrued, each participant will proceed to the Final Visit promptly without completing any other scheduled visits in order to complete the base study (as shown in Section 1.3, and Section 8.12.1.4). Additional database locks will be executed, including a second database lock after the completion of the final efficacy sample assessment for the purpose of the final efficacy analysis and a final database lock of the base study after the last participant's Final Visit in the base study for the final immunogenicity and safety analysis, respectively. Cumulative data collected from the initiation of the study will be summarized separately and a report will be written after each database lock. The base study will end after the last participant completes their Final Visit in the base study.

Extension Study

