8.5 Adverse Events, Serious Adverse Events, and Other Reportable Safety Events

The definitions of an AE or SAE, as well as the method of recording, evaluating, and assessing causality of AE and SAE and the procedures for completing and transmitting AE, SAE, and other reportable safety event reports can be found in Appendix 3.

Adverse events, SAEs, and other reportable safety events will be reported by the participant (or, when appropriate, by a caregiver, surrogate, or the participant's legally authorized representative).

The investigator and any designees are responsible for detecting, documenting, and reporting events that meet the definition of an AE or SAE as well as other reportable safety events. Investigators need to document if an SAE was associated with a medication error, misuse, or abuse.

Investigators remain responsible for following up AEs, SAEs, and other reportable safety events for outcome according to Section 8.5.3. The investigator, who is a qualified physician, will assess events that meet the definition of an AE or SAE as well as other reportable safety events with respect to seriousness, intensity and causality.

8.5.1 Time Period and Frequency for Collecting AE, SAE, and Other Reportable Safety Event Information

All AEs, SAEs, and other reportable safety events that occur after the participant provides documented informed consent, but before randomization, must be reported by the investigator if they cause the participant to be excluded from the study, or are the result of a protocol-specified intervention, including, but not limited to washout or discontinuation of usual therapy, diet, placebo, or a procedure.

Base Study:

From the time of randomization through 14 days following the first vaccination(s) and from the time of any subsequent vaccination(s) through 14 days thereafter, all AEs must be reported by the investigator. All SAEs and other reportable safety events that occur from the time of randomization through 6 months following the last vaccination must be reported by the investigator, regardless of whether the events are considered to be vaccine-related by the investigator.

Extension Study:

SAEs and death will be collected from the first dose of vaccination until 1 month after the last dose.

V503-064-03 FINAL PROTOCOL 24-SEP-2024

Base Study and Extension Study:

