9 KEY STATISTICAL CONSIDERATIONS

This section outlines the statistical analysis strategy and procedures for the study. If, after the study has begun, but prior to any unblinding/final database lock, changes are made to primary and/or secondary hypotheses, or the statistical methods related to those hypotheses, then the protocol will be amended (consistent with ICH Guideline E-9). Changes to exploratory or other non-confirmatory analyses made after the protocol has been finalized, but prior to unblinding/final database lock, will be documented in a supplemental statistical analysis plan (sSAP) and referenced in the CSR for the study. Post-hoc exploratory analyses will be clearly identified in the CSR.

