9.6.3 Statistical Methods for Safety Analyses

Safety and tolerability will be assessed by clinical review of all relevant parameters including AEs and postvaccination temperature measurements. The analysis of safety results will follow a tiered approach (Table 7). The tiers differ with respect to the analyses that will be performed. AEs (specific terms as well as system organ class terms) are either pre-specified as "Tier 1" endpoints or will be classified as belonging to "Tier 2" or "Tier 3" based on the observed proportions of participants with an event. The safety analysis strategy is summarized in Table 7.

Tier 1 Events

Safety parameters or AEs of special interest that are identified a priori constitute "Tier 1" safety endpoints that will be subject to inferential testing for statistical significance. There are no Tier 1 events for this protocol based on the global safety data on the 9vHPV vaccine.

Tier 2 Events

Tier 2 parameters will be assessed via point estimates with corresponding 95% CIs provided for the differences in the proportion of participants with events (using the Miettinen and Nurminen method [Miettinen, O. and Nurminen, M. 1985]). Membership in Tier 2 requires that at least 1% of participants in any treatment group exhibit the event.

In addition to individual events that occur in at least 1% of participants in any treatment group, the broad AE categories consisting of the proportion of participants with SAEs during

Days 1 through 15 postvaccination, vaccine-related SAEs observed any time during the study, and elevated temperatures (≥37.5°C) will be considered Tier 2 endpoints. The proportion of participants with solicited injection-site AEs (pain/tenderness, swelling, and redness) and severe injection-site AEs during Days 1 through 5 postvaccination will also be included in Tier 2 endpoints. Detailed endpoints and day ranges are summarized in Table 7.

Tier 3 Events

Safety endpoints that are not Tier 1 or 2 events are considered Tier 3 events. Only point estimates (counts and percentages) by vaccination group are provided for Tier 3 safety parameters. Safety analyses will be based on the observed data (i.e., with no imputation of missing data).

Table 7 Analysis Strategy for Safety Parameters

Safety Tier	Safety Endpoint (a)	95% CI for Comparison of 9vHPV to Placebo	Descriptive Statistics
Tier 2	Injection-site pain/tenderness, swelling, and redness during Days 1 through 5 postvaccination	X	X

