	Other injection-site AEs (incidence ≥1% of participants in either group) during Days 1 through 5 postvaccination	X	X
	Severe injection-site AEs (b) during Days 1 through 5 postvaccination	X	X
	Systemic AEs (incidence ≥1% of participants in either group) during Days 1 through 15 postvaccination	X	X
	Elevated temperatures (c) during Days 1 through 5 postvaccination	X	X
	SAEs during Days 1 through 15 postvaccination	X	X
	Serious vaccine-related AEs observed any time during the study	X	X
Tier 3	AEs by SOC		X
	Maximum intensity rating for each category of injection- site AEs		X
	Maximum intensity rating, over all systemic AEs		X
	Maximum temperatures		X
	New medical conditions		X

Abbreviations: AE=adverse event, SAE=serious adverse event, SOC=System Organ Class

- (a) The day of vaccination is counted as Day 1. Day ranges for endpoints are as follows: injection-site AEs and maximum temperatures Days 1 through 5 postvaccination; systemic AEs Days 1 through 15 postvaccination.
- (b) For the injection-site redness and swelling 0 to 2.5 cm (0 to 1 inch) will be categorized as mild, >2.5 to 5 cm (>1 inch to 2 inches) will be categorized as moderate, and >5 cm (>2 inches) will be categorized as severe.
- (c) Defined as maximum (over the follow-up period) temperature $\ge 37.5^{\circ}$ C.

Note: X = indicated summary statistic will be provided.

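### All-cause SAEs are collected through 6 months after the last dose, but the planned between-arm 95% CI for them covers only Days 1-15 after each dose; late SAEs judged unrelated, and the all-cause total, get at most counts by arm

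*Combined protocol and SAP*

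**What the plan says.** **Objective.** Section 3 lists SAEs as an endpoint of the safety objective, which sits among the primary objectives, and sets no time window.

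**Collection.** Section 4.1: "Any SAEs regardless of causality will be recorded from the time of randomization through 6 months postdose 3". Section 8.5.1 repeats this for the base study: "All SAEs and other reportable safety events that occur from the time of randomization through 6 months following the last vaccination must be reported". Neither is restricted by arm. Vaccine-related SAEs and deaths are collected throughout the study.

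**Analysis.** Section 9.4.3 lists "Systemic AEs and SAEs during Days 1 through 15 postvaccination" and, separately, vaccine-related SAEs at any time. The Tier 2 text of Section 9.6.3 names the same two SAE categories. Table 7 gives each a row with a 95% CI; the all-cause row reads "SAEs during Days 1 through 15 postvaccination".

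**Everything else.** A safety endpoint outside Tiers 1 and 2 is Tier 3 by default, and "Only point estimates (counts and percentages) by vaccination group are provided for Tier 3 safety parameters". The Tier 3 rows of Table 7 are AEs by SOC, maximum intensity ratings, maximum temperatures and new medical conditions. Section 4.1 defines the last of these as "incident medical conditions occurring outside of Days 1 to Days 15 period following each vaccination and not considered SAEs", so that row cannot hold a late SAE. Section 9.6 adds an end-of-base-study report that describes selected safety endpoints, without saying which.

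**The concern.** The collection window and the comparison window differ. For most of the period in which all SAEs are recorded, an SAE enters a comparison with a CI only if an investigator judged it related to the vaccine. A randomized placebo arm makes that judgement unnecessary: all-cause SAEs can be compared directly, which is the comparison that could show an effect nobody suspects in an individual case.

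At stake is how fully a primary safety objective is reported. No confirmatory test is affected. Deaths have a similar gap: a base-study death after Day 15 that is judged unrelated has no named row in Table 7.

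**Working it through.** **1. The plan's own SAE figures (Section 9.9.3).** Inputs: incidence 0.5%, 525 vaccine recipients.
- Chance of at least one SAE: 1 − (1 − 0.005)^525 = 0.928, against the stated 93%.
- One-sided 95% upper bound with no events: 1 − 0.05^(1/525) = 0.569%, against the stated <0.6%.

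Both reproduce. Section 9.9.3 does not say which window the 0.5% refers to.

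**2. Share of collection time with an all-cause CI.** Inputs: 15 days after each of 3 doses; dose 3 at Month 6 ± 4 weeks; 30-day months and 7-day weeks (Schedule of Activities).
- Covered: 3 × 15 = 45 days.
- Collection window = day of dose 3 + 180.

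| Dose 3 | Window (days) | Covered | Not covered |
|---|---|---|---|
| Day 152 (180 − 28) | 332 | 45/332 = 13.6% | 86.4% |
| Day 180 | 360 | 45/360 = 12.5% | 87.5% |
| Day 208 (180 + 28) | 388 | 45/388 = 11.6% | 88.4% |

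These are nominal limits. The PPE population accepts three doses within 1 year (Section 9.5.1), and dose 3 at day 365 would give 365 + 180 = 545 days.

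**3. Could the full window be reported with the primary analysis?** Inputs: 14 months of enrollment and a projected 56 months from first consent (Section 9.9.1). Even at 545 days, 14 + 545/30 = 14 + 18.2 = 32.2 months, well before 56.

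**4. How many events are involved?** Two assumptions: the 0.5% applies to the full window, and SAE risk is constant over it.
- Full window: 525 × 0.005 = 2.6 participants per arm.
- Days 1-15: 2.625 × 0.125 = 0.33, leaving about 2.3 outside.
- Chance of at least one SAE among 525 within Days 1-15: 1 − (1 − 0.005 × 0.125)^525 = 28%, against 93% over the full window.

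If SAEs cluster after doses, fewer fall outside. If the assumed full-window incidence is varied from 0.25% to 2%, the Days 1-15 probability runs from about 15% to 73%.

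**5. What the added row would show.** The Miettinen-Nurminen interval is the set of differences d with |p1 − p2 − d| / √{[r1(1 − r1)/n1 + r2(1 − r2)/n2] × N/(N − 1)} ≤ 1.96. Here r1 and r2 are the maximum-likelihood proportions under r1 − r2 = d, n1 = n2 = 525 and N = 1050.

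| Vaccine v placebo | 95% CI, percentage points |
|---|---|
| 3 v 3 | −1.16 to 1.16 |
| 8 v 3 | −0.33 to 2.47 |
| 10 v 3 | −0.01 to 2.97 |
| 11 v 3 | 0.16 to 3.21 |

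Against 3 on placebo, the interval first excludes 0 at 11 on vaccine.

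**The case against.** **This is a tiering choice, not an error.** Section 9.6.3 names no Tier 1 events, citing the global safety data on the vaccine, and there is no safety hypothesis. No section promises a CI over the whole collection window. This stands: the plan does not contradict itself, and a reader who infers a contradiction goes too far.

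**Late SAEs are not dropped.** A reader might infer that they go unanalysed, or that none has a CI. Neither is supported. Late SAEs judged vaccine-related have a Tier 2 CI at any time. The others can be tabulated by arm under the Tier 3 default, or possibly under AEs by SOC: an SAE is an AE by definition (Section 10.3.3) and that row has no day range of its own, although the systemic-AE range in the footnote may apply to it. A reader could compute a CI from such counts. What remains is that no row names the full-window total and no CI is planned for it.

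**The 1% rule could lift them into Tier 2.** Its text states no window. But it concerns individual events, needs at least 6 of 525 participants, and Section 9.6.3 sends day ranges to Table 7, which limits systemic AEs to Days 1-15. It would not produce the all-cause total.

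**Causality is judged blind.** Safety assessment is blinded (Section 8.1.9.1) and general unblinding follows the primary lock (Section 6.3.3). This limits differential bias, and no claim of bias is made here. It does not bring SAEs judged unrelated into the comparison.

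**Few events, so a CI adds little.** Partly right, as step 5 shows. But the plan already gives a CI to the shorter all-cause window, which can hold no more participants with an SAE than the full one.

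**The sSAP may cover it.** Possible. It is not among the documents reviewed, so the point concerns the protocol only.

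**Conclusion.** The point holds as a cheap improvement to the safety analysis. On nominal visit windows and 30-day months, the all-cause CI is absent for about 86% to 88% of the collection time. It would be tempting to read this as 86% to 88% of SAEs left out; the documents give no timing of SAEs, so that does not follow. The event counts in step 4 are illustrative and rest on both assumptions stated there.

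The practical gain is modest. It is an all-cause comparison, free of attribution, over the period for which the data are collected, with an interval that mainly bounds the difference. The case for adding it is that data, method and population are already in place and, on the plan's timeline, the window is complete well before the primary lock.

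**What to change.** In Section 9.4.3 and in Tier 2 of Table 7, add all-cause SAEs from randomization to 6 months after the last dose, with the risk difference and Miettinen-Nurminen 95% CI in the APaT population. Keep the Days 1-15 row. Name base-study deaths at any time as a count by arm.

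This is non-confirmatory, so under Section 9 a change made before unblinding "will be documented in a supplemental statistical analysis plan (sSAP) and referenced in the CSR for the study". If unblinding has already happened, label the analysis post hoc in the CSR, as the same section requires.

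The cost is two table rows and a few lines of text, with no new data or visits. The downside is a wide interval, which should be presented as a bound and not as evidence of no difference.
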